Except for PK determinations, all primary and secondary endpoints as above will be measured in these pubertal/postpubertal subjects after each administration. Note that for some of the pubertal/postpubertal subjects who receive further treatment, ie, those who provided PK and safety/tolerability measurements without an attack, their first icatibant-treated attack will represent their second on-study exposure to icatibant for safety analysis purposes.

In addition, for all subjects who remain enrolled in the study, a safety telephone contact will be scheduled every month to collect information concerning AEs, weight, eligibility, and HAE attacks not treated within the study.

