10.3 Analysis Populations

The following populations will be used in the analysis:

The Efficacy Population will consist of those subjects who were treated with icatibant for their first and any additional attacks.

The PK Population will consist of those subjects who were treated with icatibant and had sufficient icatibant plasma concentration time measurements to derive primary PK parameters.

The Safety Population will consist of those subjects who were treated with icatibant at least once.

All efficacy analyses will be performed on the Efficacy Population. The corresponding tabular summaries and listings will be presented by the subject stratification group at enrollment (ie, prepubertal group or pubertal/postpubertal group) and icatibant-treated attack number.

The PK analyses will be based on the PK Population.

Safety and tolerability analyses will be based on the Safety Population. All tabular summaries and listings within this population will be presented by the subject stratification group and icatibant exposure number.

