10.7 Efficacy Analyses

Efficacy analyses will be performed on the Efficacy Population. The primary efficacy endpoint is the time to onset of symptom relief measured using the investigator-reported symptom score. For the initial icatibant-treated attack, the investigator will report symptom scores at pretreatment and 1, 2, 4, and 6 hours post treatment, and at 8 hours post treatment for subjects who had not shown complete resolution of HAE symptoms at 6 hours. For subsequent icatibant-treated attacks, the investigator will report symptom scores at pretreatment and 1 and 2 hours post treatment, and every 2 hours afterwards until discharge. Eight symptoms will be assessed for abdominal and cutaneous attacks, and 13 symptoms will be assessed for laryngeal attacks. Time to onset of symptom relief is defined as the earliest time post treatment at which there is a 20% improvement in the average post-treatment symptom score with no worsening of any single component score. The median time and the 95% confidence interval will be calculated using the Kaplan-Meier methodology.

A tabular summary of the average investigator-reported symptom score and the change from baseline in the average investigator-reported symptom score will be presented by the stratification group and the icatibant exposure number. An alternative analysis will focus on the time to minimal symptoms and is defined as the time from study drug administration to the earliest time post treatment when all symptoms are either absent or mild. The median time and 95% confidence interval will be calculated using Kaplan-Meier methodology.

For individual investigator-reported symptom scores, a shift table from baseline will be presented for each post-treatment time point. The analysis will be repeated to assess shift in the individual symptom scores from the 2 hour time-point. Also, for individual symptoms that are moderate or worse at pretreatment, the median and 95% confidence interval will be presented for the time to the symptom being mild or absent.

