### 7.2 Analysis Populations

The following populations will be used in the analysis:

- The Efficacy Population will consist of those subjects who were treated with icatibant for their first and any additional attacks during the study.
- The Safety Population will consist of those subjects who were treated with icatibant at least once during the study (irrespective of the presence of an HAE attack).

All efficacy analyses will be performed on the Efficacy Population. The corresponding tabular summaries will be presented by the icatibant exposure number. For the initial icatibant exposure, the analyses will be presented by the pubertal status (Pre-pubertal vs. Pubertal/Post-pubertal) and overall; for the subsequent icatibant exposures, the analyses will be presented by the administration type (Study Site Personnel (HCP Administration) vs. Home Healthcare Providers/Patient/Parent/Legal Guardian/Caregiver (Caregiver Administration)) and overall.

Safety and tolerability analyses will be based on the Safety Population. All tabular summaries within this population will be presented by the icatibant exposure number. For the initial icatibant exposure, the analyses will be presented by the pubertal status (Pre-pubertal vs. Pubertal/Post-pubertal) and overall; for the subsequent icatibant exposures, the analyses will be presented by the administration type (HCP Administration vs. Caregiver Administration) and overall.

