### 7.8 Efficacy Analysis

Efficacy will be assessed using data from the investigator symptom score, FPS-R and FLACC. The corresponding analyses will be based on the Efficacy Population. All efficacy summaries will be presented by icatibant exposure number. For the initial icatibant exposure, the analyses will be presented by the pubertal status and overall; for the subsequent icatibant exposures, the analyses will be presented by the administration type (HCP Administration vs. Caregiver Administration) and overall.

All efficacy results will be listed by subject.

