**8.2 Changes from the Analyses Planned in the Protocol**

There was no change from the analyses planned in the protocol.

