14.1.4.3	Rescue Medications by Icatibant Exposure Number, Therapeutic Class, and Preferred Term for Icatibant Exposure Number 2 and 3 (Efficacy Population)
14.1.4.4	Rescue Medications by Pubertal Status Stratification Group, Therapeutic Class, and Preferred Term (Safety Population)
14.1.4.5	Rescue Medications by Therapeutic Class, and Preferred Term for Icatibant Exposure Number 1 (Safety Population)
14.1.4.6	Rescue Medications by Icatibant Exposure Number, Therapeutic Class, and Preferred

Table	Table Title
	Term for Icatibant Exposure Number 2 and 3 (Safety Population)
14.1.5.1	On-Study HAE Attack and Drug Exposure for Icatibant Exposure Number 1 (Efficacy Population)
14.1.5.2	On-Study HAE Attack and Drug Exposure by Icatibant Exposure Number for Icatibant Exposure Number 2 and 3 (Efficacy Population)
14.1.5.3	Drug Exposure for Icatibant Exposure Number 1 (Safety Population)
14.1.5.4	Drug Exposure by Icatibant Exposure Number for Icatibant Exposure 2 and 3 (Safety Population)
14.1.6.1	Medical History by Pubertal Status Stratification Group, System Organ Class, and Preferred Term (Efficacy Population)
14.1.6.2	Medical History by System Organ Class, and Preferred Term for Icatibant Exposure Number 1 (Efficacy Population)
14.1.6.3	Medical History by Icatibant Exposure Number, System Organ Class, and Preferred Term for Icatibant Exposure Number 2 and 3 (Efficacy Population)
14.1.6.4	Medical History by Pubertal Status Stratification Group, System Organ Class, and Preferred Term (Safety Population)
14.1.6.5	Medical History by System Organ Class, and Preferred Term for Icatibant Exposure Number 1 (Safety Population)
14.1.6.6	Medical History by Icatibant Exposure Number, System Organ Class, and Preferred Term for Icatibant Exposure Number 2 and 3 (Safety Population)
14.2	Efficacy
14.2.1.1	Time to Onset of Symptom Relief for Composite Investigator-Assessed Symptom Scores for Icatibant Exposure Number 1 (Efficacy Population)
14.2.1.2	Time to Onset of Symptom Relief for Composite Investigator-Assessed Symptom Scores for by Icatibant Exposure Number for Icatibant Exposure Number 2 and 3 (Efficacy Population)
14.2.2.1	Time to Minimum Symptoms for Composite Investigator-Assessed Symptom Scores for Icatibant Exposure Number 1 (Efficacy Population)
14.2.2.2	Time to Minimum Symptoms for Composite Investigator-Assessed Symptom Scores by Icatibant Exposure Number for Icatibant Exposure Number 2 and 3 (Efficacy Population)

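### SAP efficacy tables are indexed by exposure number, an undeclared departure from Protocol 10.3, so the exposure 2 and 3 tables mix attack orders

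*SAP*

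**What the plan says.** SAP 7.2 says of the efficacy analyses: "The corresponding tabular summaries will be presented by the icatibant exposure number". SAP 7.8 repeats it: "All efficacy summaries will be presented by icatibant exposure number". The table list in SAP 10.1.1 follows suit. The later-dose table for the primary efficacy endpoint is titled "Time to Onset of Symptom Relief for Composite Investigator-Assessed Symptom Scores for by Icatibant Exposure Number for Icatibant Exposure Number 2 and 3". Exposure 1 is split by pubertal status, and exposures 2 and 3 by who administered the dose.

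The protocol gives more than one rule:

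- Section 10.3 orders efficacy tables and listings by "subject stratification group at enrollment (ie, prepubertal group or pubertal/postpubertal group) and icatibant-treated attack number". In the same section, safety tables are ordered by exposure number.
- Section 4.1.2 says that, for subjects first dosed without an attack, "their first icatibant-treated attack will represent their second on-study exposure to icatibant for safety analysis purposes".
- Section 10.7 says that the average investigator score "will be presented by the stratification group and the icatibant exposure number", and 10.8 uses exposure number for rescue medication before relief.
- The caregiver-score paragraph of 10.7 uses a third label, the subsequent treated-attack number.

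SAP 8.2 states: "There was no change from the analyses planned in the protocol".

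**The concern.** Exposure number and treated-attack number agree only for subjects whose first dose was given during an attack. Subjects who start without an attack are always one attack behind their exposure count. A table for exposure 2 therefore puts some subjects' first treated attack beside other subjects' second.

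Efficacy on repeated use in pubertal/postpubertal subjects is a stated objective (Protocol 2.2). A reader comparing exposures 1, 2 and 3 will want to know whether response holds from one attack to the next. In the planned tables, any change or lack of change across those columns confounds attack order with starting route. No-attack starters have no earlier on-study response to compare with, because efficacy was not assessed at their first dose (Protocol 4.1.3.1). SAP 8.2 also tells the reader that nothing was changed.

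**Working it through.** **Inputs**

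- First dose during an attack: at least 20 subjects, 10 prepubertal and 10 pubertal/postpubertal (Protocol 4.1.2).
- First dose without an attack: at least 10 pubertal/postpubertal subjects (Protocol 4.1.2).
- Re-treatment: at least 10 pubertal/postpubertal subjects, from either route (Protocol 4.1.2).
- At most 3 doses per pubertal/postpubertal subject, and one per prepubertal subject (Protocol 6.2).

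The plan's own total is reproduced: 10 + 10 + 10 = 30 (Protocol 10.2). That number is empirical, so there is no power calculation to check.

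**Which rule governs each summary**

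| Efficacy summary | Protocol index | SAP index |
|---|---|---|
| Time to onset of symptom relief | none in 10.7, so 10.3: attack number | exposure number |
| Time to minimal symptoms | none in 10.7, so 10.3: attack number | exposure number |
| Individual symptom shifts and times | none in 10.7, so 10.3: attack number | exposure number |
| FPS-R times | none in 10.7, so 10.3: attack number | exposure number |
| Average investigator score | 10.7: exposure number, against 10.3 | exposure number |
| Rescue medication before relief | 10.8: exposure number, against 10.3 | exposure number |
| Caregiver score | 10.7: subsequent treated-attack number | no table listed |

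FLACC is analysed for the initial exposure only (SAP 7.8.3), so the choice of index does not affect it. The caregiver rule does not say whether a no-attack starter's first treated attack counts as the first subsequent attack.

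**How the two counts map**

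| Starting route | Exposure 1 | Exposure 2 | Exposure 3 |
|---|---|---|---|
| During an attack | attack 1 | attack 2 | attack 3 |
| Without an attack | no attack | attack 1 | attack 2 |

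**Size of the mixing in exposure 2**

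Take the planned minimum of 20 pubertal/postpubertal subjects, 10 per route, and let m of them be re-treated. The number k of first treated attacks in the exposure 2 column lies between max(0, m − 10) and min(10, m).

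| m | Range of k | Share k/m |
|---|---|---|
| 10 | 0 to 10 | 0 to 100% |
| 12 | 2 to 10 | 17 to 83% |
| 15 | 5 to 10 | 33 to 67% |
| 20 | 10 | 10/20 = 50% |

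Once m exceeds 10, some mixing is certain.

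For m = 10, assume that re-treatment does not depend on starting route. The documents give no re-treatment rate by route, so this is only an assumption. Then k is hypergeometric with mean 10 × 10/20 = 5 and a central 95% range of 3 to 7. The probability that the column is mixed is 1 − 2/C(20,10) = 1 − 2/184,756 = 0.99999.

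**After re-indexing**

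- Attack 1 holds 20 + k records (20 to 30), against 20 in exposure 1.
- Attack 2 holds the attack-first subjects' exposure 2 records plus the no-attack starters' exposure 3 records.
- Attack 3 can hold attack-first subjects only, because a no-attack starter reaches at most two treated attacks within three doses.

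**Does another planned table separate the two?** No. Exposures 2 and 3 are split by administration type, not by starting route, and SAP 9.6 plans no subgroup analysis.

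**The case against.** The strongest reply is that the SAP follows a choice the sponsor had already made. The summary of changes for Amendment 4 shows attack number being replaced by exposure number in 10.7 and 10.8, which leaves 10.3 looking like text that was not updated. The repeat-dose objective is itself worded in terms of exposures, and the re-treatment target counts treatments. Indexing by dose answers that objective, and it keeps no-attack starters in the exposure 3 column, whereas an attack 3 column would lose them.

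Much of this stands. A reader might infer that the protocol uniformly requires attack number and that the SAP contradicts it throughout. The documents do not support that: for the average investigator score and for rescue medication the SAP agrees with 10.7 and 10.8. What does not follow is that exposure number was adopted for all efficacy. Section 10.3 still says otherwise, and neither 10.7 nor 10.8 supplies another index for the primary efficacy endpoint.

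A reader might also infer that moving no-attack starters' first treated attacks into an attack 1 column, from 20 records to as many as 30, would tighten the first-attack estimate by the square root of the sample size. That is not shown either. The estimate is a Kaplan-Meier median on a coarse assessment grid. Investigator scores for later attacks exist only for subjects treated at the site (Protocol 7.11.1.1). The schedule also differs: 1, 2, 4, 6 and sometimes 8 hours initially, against 1 and 2 hours and then every 2 hours as needed for subsequent attacks.

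Finally, efficacy and dosing are listed by subject, so attack order can be rebuilt. That limits the harm but does not repair the summary tables.

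**Conclusion.** The point holds as an inconsistency between protocol sections, an undeclared departure from 10.3 and a confounded set of summary tables. For time to onset of symptom relief, time to minimal symptoms and the other investigator-score and FPS-R summaries to which 10.7 gives no index, the SAP departs from the only protocol rule that applies, and SAP 8.2 is inaccurate. For the average investigator score and rescue medication the conflict lies within the protocol itself.

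Exposure 2 mixes first and second treated attacks: 10 of 20 if all 20 planned pubertal/postpubertal subjects are re-treated, and anywhere from 0 to 100% if only 10 are. Exposure 3 mixes second and third. These figures rest on the planned minimum of 10 subjects per starting route. The numbers actually re-treated by route are not in the documents. No type I error, power or sample size is affected, because efficacy is descriptive. What is lost is a clear reading of response across successive attacks.

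**What to change.** 1. Reconcile Protocol 10.3 with 10.7 and 10.8, so that each efficacy summary has one stated index. Define how the subsequent-attack number in the caregiver paragraph is counted.
2. In SAP 7.2, 7.8 and the 14.2 tables, present time to onset of relief, time to minimal symptoms and the other efficacy results by treated-attack number, with a flag for a prior no-attack dose. At minimum, split the exposure 2 and 3 tables by whether the first dose was given during an attack. The existing exposure tables can stay alongside.
3. Keep exposure number for safety.
4. Record in SAP 8.2 any efficacy summary still presented by exposure number where 10.3 is the only rule.
5. Footnote any pooled first-attack summary: subsequent attacks follow a different assessment schedule, and home-treated attacks have no investigator score.

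The cost is one derived variable and some additional tables. Attack details, dosing and scores are already in listings 16.2.4.5, 16.2.5 and 16.2.6.1. The downside is small cells, thinner still if the administration-type split is kept, and an attack 3 column that can contain only attack-first subjects. Retaining the exposure 1 table keeps the link to the initial-treatment results already reported.

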3 STUDY ENDPOINTS

3.1 Primary Endpoints

Primary endpoints:

The PK profile of icatibant after a single SC injection in pediatric subjects (in prepubertal children with an acute attack of HAE and pubertal/postpubertal children with or without an acute attack of HAE).

The tolerability and safety of SC icatibant as assessed by injection site reactions, adverse events (AEs), vital signs, electrocardiogram (ECG) recordings, physical examination, clinical laboratory parameters (serum chemistry [including liver function tests], hematology, urinalysis), reproductive hormone levels, and immunogenicity (presence of anti-icatibant antibodies).

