4 INVESTIGATIONAL PLAN

4.1 Overall Study Design and Plan

4.1.1 Study Design

This is an open-label, non-randomized, single-arm study to evaluate the PK, tolerability, and safety, including effects on reproductive hormones, of a single SC administration of icatibant in pediatric subjects with HAE.

The study will enroll children and adolescents from 2 to less than 18 years of age, divided into 2 groups: prepubertal (Tanner stage I) and pubertal/postpubertal (Tanner stages II to V).

At least 10 prepubertal children and at least 20 adolescents (including 10 treated during a HAE attack) must be enrolled in the study.

Subjects who reach their 18th birthday during the course of follow-up are allowed to remain in the study and receive subsequent treatments with icatibant according to the protocol. Subjects will continue to receive icatibant as a single, weight-adjusted dose of 0.4 mg/kg up to a maximum of 30 mg administered as an SC injection.

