4.1.2 Study Methodology

A subject's classification as prepubertal or pubertal/postpubertal will be determined at screening and, if classified as prepubertal at screening will have their pubertal status reassessed at the time of their first icatibant-treated attack visit.

Initially, enrollment and dosing of pubertal/postpubertal subjects will precede that of prepubertal subjects. After the first 4 subjects in the pubertal/postpubertal group have been treated with icatibant (whether during or in the absence of attack), PK, safety/tolerability, and efficacy (as appropriate) will be reviewed by an independent Data and Safety Monitoring Board (DSMB). The DSMB review of the first 4 subjects shall be completed prior to continuing enrollment of additional pubertal/postpubertal subjects, treatment of second and third HAE attacks in pubertal/postpubertal subjects, and initiating enrollment of subjects in the prepubertal group.

Initial Icatibant Treatment

After a qualifying screening period, the PK, safety/tolerability, and efficacy of treatment with SC icatibant will be evaluated in at least 20 subjects (10 prepubertal and 10 pubertal/postpubertal subjects) who present with cutaneous, abdominal, or laryngeal symptoms of an acute attack of HAE. Subjects should initiate treatment with icatibant within 12 hours of the onset of symptoms; however, there are no prespecified attack severity criteria that are required for treatment. Subjects with attacks considered to be mild, moderate, or severe are all potentially eligible to receive treatment with icatibant.

The PK and safety/tolerability of SC icatibant will be evaluated in at least 10 additional pubertal/postpubertal subjects who meet screening criteria, but receive treatment with SC icatibant in the absence of a current acute HAE attack.

Subjects will receive treatment with a single SC administration of icatibant on Day 1 and will be monitored closely in the hospital/study center for at least 6 to 8 hours after treatment. Subjects will undergo PK and safety assessments; efficacy assessments will be performed if treatment occurs during an acute HAE attack. All subjects will have serum reproductive hormone measurements.

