5 STUDY POPULATION SELECTION

5.1 Study Population

The study will enroll a sufficient number of children and adolescents with HAE to ensure study completion of 30 subjects. The study population to provide efficacy, PK, and safety/tolerability measurements will consist of at least 20 subjects from 2 to less than 18 years of age, at least 10 of whom are prepubertal and at least 10 of whom are pubertal/postpubertal at the time of their first icatibant-treated acute cutaneous, abdominal, or laryngeal attack of HAE. An additional 10 subjects who are pubertal/postpubertal at the time of enrollment, but who are not experiencing a current HAE attack, will provide PK and safety/tolerability measurements only.

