10.5.1.2 Compartmental Modeling Using Population Methods

Nonlinear mixed effects modeling will be used to define individual subject profiles and if possible, parameter estimates. The structural PK model will be developed and validated using PK information obtained from adult subjects and will enable delineation of the impact of age-dependent changes on icatibant disposition. Development of this model will allow for characterization and better prediction of the dose-concentration-exposure relationship for icatibant in pediatric subjects. Population PK modeling will be performed with nonlinear mixed effect modeling software (eg, NONMEM, Globomax LLC or WinNonMix, Pharsight Corp.). The program will estimate the inter- and intra-individual variability of PK parameter estimates. Both weight-normalization and allometric scaling principles will be evaluated. For selecting preliminary meaningful covariates the general additive model (GAM) analysis will be used. Variables to be considered will include (but are not limited to): age, sex, ethnicity, total and lean bodyweight (TBW, LBW), body mass index (BMI), and body surface area (BSA).

Monte Carlo simulation experiments based on the model(s) developed above may be performed by a validated simulation software program (eg, Trial Simulator, Pharsight Corp.) to assess the response patterns for various dosage regimens of icatibant treatments in the pediatric population.

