### 2.2 Background

This is an open-label, non-randomized, single-arm study to evaluate the PK, tolerability, safety including reproductive hormone assessments, and efficacy of a single SC administration of icatibant in approximately 30 pediatric subjects with HAE during an initial acute attack. Details of the study design, rationale, and procedures are documented in [Protocol HGT-FIR-086](#).

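### First-dose safety tables put adolescents treated in an attack and those treated without one in one column, so change-from-pretreatment summaries carry attack resolution unequally across the pubertal-status columns

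*SAP*

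**What the plan says.** The design has three first-dose cohorts. Protocol 4.1.1 states: "At least 10 prepubertal children and at least 20 adolescents (including 10 treated during a HAE attack) must be enrolled in the study". Protocol 4.1.2 describes the rest of the adolescents as "at least 10 additional pubertal/postpubertal subjects who meet screening criteria, but receive treatment with SC icatibant in the absence of a current acute HAE attack", and they follow their own schedule (Protocol Appendix 1, against Appendix 2 for the initial attack). The primary PK endpoint in Protocol 3.1 names the distinction: "in prepubertal children with an acute attack of HAE and pubertal/postpubertal children with or without an acute attack of HAE".

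The analysis has two groups. SAP 7.2 defines the Safety Population as subjects "treated with icatibant at least once during the study (irrespective of the presence of an HAE attack"), and sets the first-dose columns: "For the initial icatibant exposure, the analyses will be presented by the pubertal status (Pre-pubertal vs. Pubertal/Post-pubertal) and overall". SAP 7.9 repeats this for all safety summaries. Protocol 10.3 and 10.6 also tabulate by pubertal stratification group and exposure number only, so the SAP is following the protocol here.

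Nothing else in the SAP separates the cohorts. Covariate adjustment (9.1), subgroups (9.6) and sensitivity analyses (9.7) are all ruled out. Vital signs, laboratory values and reproductive hormones are summarised as observed values and changes from pretreatment (SAP 7.9.4, 7.9.6, 7.9.7), and their tables are listed for the Safety Population only.

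**The concern.** Protocol 1.1 describes HAE attacks as self-limiting. In a subject dosed during an attack, the Day 1 pretreatment vital signs, laboratory values and hormones are in-attack values. A later change from them can contain recovery from the attack as well as any effect of icatibant, and there is no control arm to separate the two.

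The adolescents dosed without an attack do not have this problem on Day 1, but the tables average them with adolescents who do. Two readings suffer:

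- The overall and pubertal columns mix dose effect and attack resolution in proportions the reader cannot see.
- Side-by-side reading of the prepubertal and pubertal columns confounds age group with attack status, because the first column is entirely in-attack and the second only partly.

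Safety and tolerability, including reproductive hormones, is a primary endpoint, and Protocol 4.2 singles out effects on reproductive development. The affected tables therefore matter to the trial's purpose.

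**Working it through.** **Inputs**
- At least 10 prepubertal subjects, all in attack, and at least 10 adolescents in attack (Protocol 4.1.1, 3.1).
- At least 10 adolescents without an attack (Protocol 4.1.2; Protocol 5.1: "An additional 10 subjects who are pubertal/postpubertal at the time of enrollment, but who are not experiencing a current HAE attack").
- d = shift in a change-from-pretreatment measure caused by attack resolution alone. The documents give no value, so d is an assumption. It is taken as equal in both age groups and zero without an attack. Drug and age effects are set to zero to isolate the artefact.

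**The plan's own figure.** 10 + 10 + 10 = 30 subjects, of whom 10 + 10 = 20 are pubertal/postpubertal. This reproduces the planned numbers in SAP 4.5, which rest on no formal calculation.

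**Share of no-attack subjects per planned column**
- Prepubertal: 0/10 = 0%
- Pubertal/postpubertal: 10/20 = 50%
- Overall: 10/30 = 33%

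**What the columns show at the minima**
- Prepubertal: d
- Pubertal/postpubertal: (10 × d + 10 × 0)/20 = d/2
- Overall: (20 × d + 10 × 0)/30 = 2d/3
- Apparent prepubertal-pubertal difference: d − d/2 = d/2

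For d = 0.25, 0.5, 1.0 and 1.5 SD, that difference is 0.125, 0.25, 0.5 and 0.75 SD.

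**Other adolescent splits.** The cohort sizes are minima. With a adolescents in attack and n without, the apparent difference is d − d × a/(a + n) = d × n/(a + n).

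| Attack:no-attack (assumed) | Apparent difference |
|---|---|
| 20:10 | 10/30 = 0.33d |
| 15:10 | 10/25 = 0.40d |
| 10:10 | 10/20 = 0.50d |
| 10:15 | 15/25 = 0.60d |

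**After splitting the column.** Prepubertal against pubertal in-attack gives d − d = 0, so an equal resolution shift cancels. Pubertal in-attack against pubertal no-attack gives d − 0 = d, so the shift becomes visible.

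**Precision cost**
- 95% half-width for a difference in two column means, t × √(1/n1 + 1/n2) in SD units: 10 v 20, 2.048 × 0.387 = 0.79; 10 v 10, 2.101 × 0.447 = 0.94.
- Two-sided exact 95% upper limit when no event is seen, 1 − 0.025^(1/n): 16.8% for n = 20; 30.8% for n = 10.

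**Where the mechanism applies.** It needs a Day 1 pretreatment value taken in the attack, which vital signs (post-dose at 1 h and 6 or 8 h), laboratory values (6 h) and hormones (6 h) have. For second and third doses, the baseline is a site visit within 6 months before treatment (Protocol 8.4.1), so Day 8 and Day 90 changes there need not start from an in-attack value. However, those doses have no Day 1 post-dose vital signs, laboratory or hormone samples (Protocol Appendix 3). The no-attack cohort is therefore unique for the Day 1 changes.

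**The case against.** The strongest reply is that no age comparison is planned. There is no hypothesis test or model (SAP 9.1, 9.3, 9.5), pubertal status is the protocol's own stratification, and hormone reference ranges depend on it (SAP 7.9.7). This stands: the confounding affects how descriptive columns are read, not a p-value or error rate.

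A second reply is that cells of 10 are too small to split. This is weak. For second and third doses, SAP 7.2 already splits by who administers the drug, although Protocol 4.1.3.2 looks for only at least 10 adolescents treated three times; an even split would leave about 5 per column. The no-attack group is a planned cohort, not a subgroup found in the data.

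A third reply is timing. First-dose results are already reported (Protocol 1.2.2) and an interim analysis has been done (SAP 9.3), so a split made now is not pre-specified with respect to those data. This stands and has to be disclosed.

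A reader might also infer more than the documents support:

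- *That the no-attack information is lost.* SAP 7.9 lists all safety outcomes by subject, and drug administration and attack details are listed too, so attack status can be recovered.
- *That every safety table has an in-attack baseline.* ECG is compared with screening (SAP 7.9.5), injection-site reactions have no pretreatment value, and antibody status is any positive result after pretreatment (SAP 7.9.3).
- *That AE rates are distorted to a known degree.* The documents give no rates by attack status, and worsening of a treated attack is not an AE unless serious (Protocol 7.17.1.1).
- *That the PK models leave out attack status.* The covariate list is open-ended ("Variables to be considered will include (but are not limited to): age, sex, ethnicity, total and lean bodyweight (TBW, LBW), body mass index"), and PK has a separate plan not available here (SAP 7.1).
- *That efficacy rests on about 30 in-attack subjects.* SAP 2.2 does say "efficacy of a single SC administration of icatibant in approximately 30 pediatric subjects with HAE during an initial acute attack", but SAP 4.1 gives at least 20 in attack plus at least 10 without, and SAP 7.2 limits the Efficacy Population to subjects treated for attacks. This is a wording slip.

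**Conclusion.** The point holds for the first-dose summaries of vital signs, laboratory values and reproductive hormones. As planned, attack resolution of size d would appear as an apparent prepubertal-pubertal difference of d/2 at the minimum cohort sizes (0.33d to 0.60d over the assumed splits) and as 2d/3 in the overall column. The size rests on an assumed d, equal across age groups and zero without an attack; whether d is material for any given measure cannot be judged from the documents. The no-attack cohort is the only group whose Day 1 changes cannot reflect attack resolution. It remains uncontrolled, so its changes are free of that one explanation, not of all others. This is a worthwhile improvement to descriptive tables. It invalidates no planned inference, and no data are missing.

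**What to change.** - In SAP 7.2 and 7.9 (and Protocol 10.3 and 10.6, if amended), split the pubertal/postpubertal column of the first-dose vital-sign, laboratory and hormone tables into *treated during attack* and *treated without attack*. Keep the pooled pubertal and overall columns. Do the same in the first-dose AE tables, for description only.
- State that the like-for-like comparison with prepubertal subjects is the in-attack adolescent column, and that Day 1 changes in the no-attack column cannot reflect attack resolution.
- Record the split in SAP 8.2, which now reports no change from the protocol's analyses, and label it as added after the interim analysis of first-dose data.
- As a minor correction, align SAP 2.2 with SAP 4.1.

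The cost is two extra columns in existing tables and no new data. The cells hold about 10 subjects and support description only: half-widths grow from about 0.79 to 0.94 SD for a two-column difference, and the upper limit after zero events rises from 16.8% to 30.8%.
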